Background: Obesity is increasingly common in childhood and adolescence and is associated with high rates of abnormal cholesterol and high blood pressure, type 2 diabetes and cardiovascular disease. Studies suggest that regular physical activity can reduce cardiovascular risk factors in children. Despite evidence of its benefits, exercise training prescribed by physicians for overweight children is traditionally vague, developmentally inappropriate, and/or fraught with psychological barriers. There has been recent increased interest in the use of interactive new technologies to promote physical activity, prevent or reverse unhealthy weight and improve physical fitness in youth. **Objective:** To determine whether exercise counseling with BodyMedia, an online interactive accelerometer, has an effect on physical activity levels, fitness levels, and cardiometabolic measurements in pediatric patients with cardiovascular risk factors. **Design:** A randomized controlled pilot study of children at increased risk for atherosclerosis comparing exercise prescription combined with BodyMedia to a control group receiving physician counseling alone (standard of care). **Measures:** All study patients will be assessed at baseline and at the end of the study period directly for energy expenditure and physical activity using accelerometry; physical fitness will be assessed by standard VO₂ stress at the same time periods. Available blood pressure and lipid levels will be gathered from clinical encounters, and self-efficacy will be evaluated by questionnaires. **Primary Hypothesis:** This interactive technology coupled with support from exercise specialists will increase the energy expenditure of our patients over standard of care provider counseling. **Secondary hypotheses:** There will be greater improvement in measured physical fitness, lipid profiles, blood pressure, arterial stiffness, BMI, BMI percentile, and self-efficacy in the intervention group compared to control.

1. Specific Aims /Objectives

Primary aim: This pilot study seeks to compare the change in energy expenditure and fitness levels of patients seen in the Children's Hospital Preventive Cardiology program receiving standard of care provider exercise counseling to similar patients receiving FITT (Frequency, Intensity, Time, Type) exercise prescription and counseling combined with BodyMedia supported by an online interactive tool.

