- Our primary hypothesis is that this interactive technology coupled with support from a exercise specialist will increase the energy expenditure of our patients over standard of care provider counseling
- Secondary hypotheses include greater improvement in measured physical fitness, lipid profiles, blood pressure, arterial stiffness, BMI, BMI percentile, and self-efficacy in the intervention group compared to control.

2. Background and Significance

Obesity is increasingly common in childhood and adolescence, and is a major threat to health. Obese pediatric patients have high rates of abnormal cholesterol and high blood pressure (AHA 2010) and childhood obesity is predictive of type 2 diabetes and cardiovascular disease (CVD) (Morrison 2008). Studies suggest that regular physical activity can reduce cardiovascular risk factors in children. Exercise training can improve cardiovascular risk factors (Ferguson 1999) and the intra-individual clustering of cardiometabolic risk factors (Reinehr 2009), in individuals with obesity (Klijn 2007) and diabetes (Caranti 2007). Reduction in risk factors may occur both by direct effects (e.g. blood pressure reduction, increasing HDL), and indirectly through weight reduction. National guidelines recommend that children accumulate at least 60 minutes per day of moderate to vigorous physical activity on most days of the week (CDC 2010), based on evidence of physiologic benefits (Strong 2005). However, most children are not meeting these recommendations; declining levels of physical fitness among children and adolescents contribute to the obesity-associated health risks of future generations (American Heart Association, 2005).

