counseling by a pediatric exercise physiologist + interactive accelerometer, or office provider counseling (standard of care). The intervention group will be asked to continue to wear the accelerometer everyday (most waking hours) and log their activity by regularly (3 times a week) uploading the device for a period of 3 months, use of the internet must be supervised by a parent or guardian. Their activity will be monitored via the online site on a regular basis by study personnel and feedback will be provided at least once a week through email and/or phone calls. At the end of the intervention all participants will be asked to again wear the accelerometer for 1 week to assess physical activity, and complete questionnaires assessing attitudes towards and self-efficacy around physical activity. Lipid levels and blood pressures, when obtained for clinical visits in Preventive Cardiology Clinic, will be evaluated for change over the course of the intervention. Participants will be given a non-invasive pulse wave velocity test. Pulse wave velocity testing is a painless non-invasive test to evaluate the time it takes for blood to move from the heart to the rest of the body. In practice, this involves using a fingertip probe placed lightly on the brachial artery – the internal aspect of the elbow, the carotid artery – side of the neck, and the femoral artery – groin area. This final measurement is easily performed through light clothing. In order to coordinate the timing of the pulse wave, four EKG electrodes are placed on the patient. The entire procedure takes about 15 minutes in experienced hands. There is no risk involved in this non-invasive procedure. It is less painful than a blood pressure measurement. The research study will require 2 visits to the Preventive Cardiology Clinic in Boston or Waltham, based on their preference. Each visit may take up to 1-1.5 hours.

b. Patient Selection and Inclusion/Exclusion Criteria

A sample of 60 patients at increased risk for atherosclerosis will be recruited from Preventive Cardiology.

Inclusion criteria:

Subjects will be eligible for enrollment based on the following criteria:

- 1) Patients at increased risk of atherosclerosis based on lipid profiles (TC > 199 mg/dL, HDL < 40 mg/dL, LDL > 129 mg/dL, blood pressure (SBP or DBP > 90th percentile), obesity (>85%BMI)
- 2) Ages 13-21 years
- 3) Reporting an average of less than 60 minutes per day of moderate to vigorous exercise most (5) days of the week.

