Arterial Stiffness: Pulse wave velocity is a measure of the speed of transit of the pulse generally measured from the carotid to the femoral artery using ECG gated measurements of the peak pulse impulse. NIHem Hemodynamic Acquisition system quantifies pulse wave velocity (PWV), as well as other measures of arterial hemodynamics. Carotid- femoral pulse wave velocity has emerged as the "gold standard" index of aortic stiffness. The NIHem system has been previously validated to resolve pulse wave analysis in time or frequency domains and has been used extensively in the NIH/ NHLBI's Framingham Heart Study to at more than 12,000 participant visits with 90% reproducibility. Median time to complete a full set of measurements is roughly 15 minutes.

Questionnaires: A pre and post exercise questionnaire, adapted from the Youth Risk Behavior Survey and from the Trial of Activity for Adolescent Girls (Dishman 2009) will be administered. Questions will assess self efficacy, social support, perceived barriers and enjoyment related to exercise.

Laboratory testing: All study subjects will undergo testing including a fasting lipid profile consisting of TC, HDL, low-density lipoprotein (LDL), and triglycerides (TG) concentrations. Additional labs that will be collected, if available, include liver transaminase alanine aminotransferase (ALT), C-reactive protein (CRP), a relatively stable measure of the inflammatory state known to be associated with cardiovascular risk in adults, glycosylated hemoglobin (Hgn A1C) to assess long term glucose homeostasis. Fasting insulin and glucose will also be collected, if performed for clinical reasons by Preventive Cardiology or the patient's primary care.

Height, Weight, and Blood Pressure measurements will be obtained according to clinical practice guidelines. Blood pressure will be measured in a standardized manner in the right arm after 5 minutes of quiet sitting by automatic blood pressure device. One measurement of height (nearest 0.1 cm) and weight (nearest 0.1 kg) will be obtained. Body mass index (calculated as weight/height^2 [kg/m²]) using CHB EMR/PowerChart) will be used to estimate excess overall adiposity. Additional measures of auscultative blood pressure will be collected if available. [name] will interpret the anthropometric data.

f. Data Collection Methods, Assessments and Schedule (what assessments performed, how often)

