Data will be collected by study personnel including exercise physiologist, research fellow, head EKG technician and exercise student intern. The research team will assure that all data is collected. The data will be recorded in a de-identified manner using study IDs only. The key between participants and study IDs will be stored in a password protected electronic file. The data will be entered using a standard data management program (REDCap) on an ongoing basis. The data will be examined systematically for quality control and data cleaning purposes during the course of the study and again at the end. A portion of the data forms will be double entered for quality assurance purposes. The assistance of the Clinical Research Program will be solicited for technical support in these areas.

b. Quality Control Method The data will be examined systematically for quality control and data cleaning purposes quarterly during the course of the study and again at the study end prior to analysis.

c. Data Analysis Plan

The primary test of hypothesis is the comparison of change in Energy Expenditure (ΔEE) between baseline and final visit (12 weeks) in children receiving FITT Counseling plus BodyMedia as compared to children receiving physician counseling alone (standard of care/control). A two sample t-test will be used for this comparison. In the event of non-normality, the Wilcoxon rank sum test will be used. Secondary outcomes will be analyzed similarly. Linear regression will be used to adjust for any suspected confounding. In all tests, a two tailed p-value <0.05 will be considered statistically significant.

d. Study sample size and power considerations. . A total sample size of 40 (20/group) would provide adequate power to detect differences in physical activity counts as small as 0.9 standard deviations. Based on previous studies and clinical experience we expect $\leq 30\%$ attrition rate over 6 months: 30 patients per study group will be enrolled to ensure ≥ 20 per group complete the study

e. Study Organization

The study group will meet monthly to review progress and results of the study. Dr. [name] and [name] will review testing results as they are received. The Clinical Research Team will oversee recruitment and study activities for the Study.

f. Data and Safety Monitoring Plan

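### Section 5.c lets every secondary outcome be declared significant at p<0.05: about a 16–24% chance of a false claim of benefit if independent, with the primary test unaffected

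*Combined protocol and SAP*

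**What the plan says.** Section 5.c identifies a single primary comparison: "The primary test of hypothesis is the comparison of change in Energy Expenditure", baseline to 12 weeks, intervention against control. It says that secondary outcomes are handled in the same way, and closes with the decision rule "In all tests, a two tailed p-value <0.05 will be considered statistically significant".

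Section 1 words the secondary outcomes as directional hypotheses: "Secondary hypotheses include greater improvement in measured physical fitness, lipid profiles, blood pressure, arterial stiffness, BMI, BMI percentile, and self-efficacy". No section ranks them, adjusts for their number or calls them exploratory.

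The primary is worded in two ways. The primary aim in section 1 is to "compare the change in energy expenditure and fitness levels of patients". The primary hypothesis is that the intervention "will increase the energy expenditure of our patients over standard of care provider counseling", with no mention of fitness, and fitness then appears first among the secondary hypotheses.

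**The concern.** The plan is not silent here. It gives a rule and applies it to every test. Because each secondary outcome is written as an expected improvement, a p<0.05 in the right direction would read as confirming a stated hypothesis. The plan expects about 20 completers per group and has at least seven secondary outcomes, so an isolated significant result is quite likely by chance alone. If ΔEE were null and one lipid fraction, blood pressure or pulse wave velocity result fell below 0.05, the report could call that result significant without departing from its plan.

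**Working it through.** **Inputs**

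- Threshold per test: 0.05 two-sided (section 5.c), so 0.025 in the direction of benefit.
- Named secondary items (section 1): fitness, lipid profile, blood pressure, arterial stiffness, BMI, BMI percentile, self-efficacy. That is 7.
- Lipid components (section 4.e, laboratory testing): "a fasting lipid profile consisting of TC, HDL, low-density lipoprotein (LDL), and triglycerides (TG) concentrations". That is 4.
- Blood pressure components: 2. The split comes from the inclusion criteria in section 4.b, "blood pressure (SBP or DBP > 90th percentile", not from an outcome definition.
- Expanded count: 4 lipids + 2 pressures + fitness + pulse wave velocity + BMI + BMI percentile + self-efficacy = 11. Table 1 has no row for VO₂ testing, although the abstract says it is done at both time points. Without it the count is 10.
- Not counted: ALT, CRP, HbA1c, insulin and glucose, which are collected but are not named in the secondary hypotheses.

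**The plan's own figure**

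Section 5.d states adequate power for 0.9 SD with 20 per group, without naming the power. I take the 0.9 SD to apply to ΔEE, although 5.d refers to activity counts. The noncentrality is 0.9 × √(20/2) = 2.85. At two-sided 0.05, power is 81.2% by the normal approximation and 79.2% by the t distribution, so the statement holds if adequate means about 80%. With 30 enrolled per group and 30% attrition, 30 × 0.7 = 21 remain, which meets the target of 20.

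**Chance of at least one false positive among the secondaries**

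The intervention is assumed to have no effect on any outcome, and the tests are taken as independent. For k tests the chance is 1 − 0.95^k in either direction and 1 − 0.975^k in the direction of benefit.

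| Secondary tests | Either direction | Benefit direction |
|---|---|---|
| 1 | 5% | 2.5% |
| 7 (named items) | 30.2% | 16.2% |
| 10 (expanded, no VO₂) | 40.1% | 22.4% |
| 11 (expanded) | 43.1% | 24.3% |

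**Effect of correlation**

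These outcomes are correlated, but the documents give no correlations, so the values below are assumptions. The figures come from simulated two-sample t-tests with 20 per group, 40,000 replicates, and equal correlation between all outcomes, each signed so that positive means benefit.

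| Correlation | 11 secondaries: either / benefit | 12 tests with primary: either / benefit |
|---|---|---|
| 0.3 | 38% / 19% | 40% / 21% |
| 0.5 | 31% / 15% | 32% / 16% |
| 0.7 | 23% / 11% | 24% / 12% |

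At a correlation of 0.9, the 12-test figures fall to 14% and 7%. With stronger links assumed within the lipids, within blood pressure, between the two BMI measures and between energy expenditure and fitness, and 0.2 elsewhere, they are 39% and 20%.

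**The case against.** The strongest case against the point is that this is a pilot with its outcomes already ranked. One test is designated primary, its error rate is 5%, and nothing in the secondary list changes that. No section says the trial succeeds on a secondary result or that one would rescue a null primary. Calling a result statistically significant is not the same as claiming efficacy. All of this stands, and it limits the point to how secondary results may be described. Pilot status does not remove the point, because it argues for estimation and exploratory labelling, and section 5.c does the opposite.

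The count of 11 is also open to challenge. Section 5.c does not say that each lipid fraction is tested, and the systolic/diastolic split is borrowed from eligibility. This stands too, which is why the range starts at the seven named items.

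Two stronger readings are tempting, and the documents support neither:

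- A reader might infer a 43% chance of a false claim of benefit. That figure counts results favouring control as well, and assumes 11 independent tests. The corresponding figure for benefit is 24%, and positive correlation lowers it.
- A reader might infer from the primary aim that energy expenditure and fitness are co-primary, so that the primary error rate is 1 − 0.95² = 9.75%. The primary hypothesis and the primary test name energy expenditure only, and fitness is listed as a secondary hypothesis. The phrase in the aim is an inconsistency, not a second primary test.

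**Conclusion.** The point holds for the secondary outcomes only. Under the stated rule, an intervention with no effect has a 30–43% chance of at least one significant secondary result in either direction if the tests are independent. In the direction of benefit the chance is about 16–24% if independent, and roughly 12–21% for 12 tests (primary included) at assumed equal correlations of 0.7 to 0.3. The comparison is 2.5% for a single test. The figures rest on no effect on any outcome, 7 to 11 secondary tests, and correlations that the documents do not supply.

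The primary test is sound in this respect. This is a low-cost improvement to what the report may claim and does not threaten the trial's main conclusion.

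**What to change.** In section 5.c, replace the blanket rule with wording such as: *Statistical significance (two-sided 0.05) will be claimed only for the change in energy expenditure. All secondary outcomes will be reported as between-group differences with 95% confidence intervals and are exploratory.* The label is needed as well as the intervals, since an interval that excludes zero would otherwise be read as a significance claim.

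In section 1, move fitness from the primary aim to the secondary aims. This is a consistency edit, because the primary hypothesis and primary test already exclude it.

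The cost is two short edits and the loss of any statement that a secondary result is statistically significant. No patients, visits or measurements are added, and power for ΔEE is unchanged at about 79% for 0.9 SD with 20 per group. I do not suggest a formal adjustment across outcomes: at 0.05/12 = 0.0042 per test, power for a 0.9 SD difference would fall to 43%, too high a price in a pilot of this size.

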Forty patients with hyperlipidemia, overweight/obesity and/or HTN received FITT counseling in addition to standard care counseling by physicians during their visit in the Preventive Cardiology Clinic. Subjects were divided into "compliant" and "non-compliant" groups on the basis of information gleaned from their follow up clinic visit notes. Those that were compliant showed improvement in their lipid profile, BMI and physical activity levels. In contrast, non-compliant patients either showed no change or worsened cardiovascular risk factors. We concluded that when children with cardiovascular risk factors adhere to an exercise prescription, improvements are often achieved, and successful weight loss is sometimes realized. Unfortunately, poor compliance with exercise prescriptions was again common, and limited the effectiveness of this therapeutic intervention.

4. Design and Methods

a. Study Design

A randomized controlled pilot study comparing exercise prescription based on the FITT principle combined with BodyMedia, an online supported accelerometer, to a control group receiving physician counseling alone (standard of care). All participants will wear an accelerometer to measure physical activity for one week at the start of the intervention. At the end of that week, patients who have worn the accelerometer for more than 8 hours per day for at least 3 days will be randomly assigned to either FITT

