- 4) Regular access to the internet with the capacity to download the device
- 5) Commitment on the part of a parent to supervise internet access as part of this protocol

Exclusion criteria:

- 1) Unable to exercise based on physician recommendations or medical conditions
- 2) Unable/unwilling to complete requirements of the research study including consent and assent.
- 3) Not proficient in English

c. Recruitment Methods

- i. HOW, WHERE and WHEN will potential subjects be recruited?

Patients will be screened for potential participation based on previous Preventive Cardiology clinic visit notes. If the child appears to meet the eligibility criteria for the study, a recruitment letter and opt-out postcard will be sent with a pre-clinic mailing at least 2 weeks prior to the scheduled visit. If patients indicate non-participation preference by returning the postcard, they will not be contacted about the study. If the postcard is not returned, study personnel will approach the patient during their clinic visit to discuss participation, eligibility and exercise habits. In addition, we will approach patients in the Lipid Clinic in Boston and Waltham that did not receive a mailing, but are potentially eligible for the study. If eligible we will obtain consent for enrollment into the study. A study visit will be scheduled during the initial clinic visit. The research study will require 2 visits to the Preventive Cardiology Clinic in Boston

or Waltham, based on participate preference. Each visit may take up to 1.5 hours. A gift card or cash incentive of \$15.00 will be given to the patient when they qualify and arrive at their first study visit. If patient requires more time to think about the study and request a phone call follow up, a study staff member will contact them via phone to discuss study participation. Phone calls will only be made if the patient has requested to be contacted at a later time and expressed interest in the study. If potential participant decides they would like to enroll in the study, verbal consent will be obtained and the device will be mailed to patient. Written consent will be obtained during the first study visit. Patients that are not interested in the study at the time of their clinic visit will be tracked in a spreadsheet and will not be contacted again.

- ii. WHAT recruitment methods and materials (e.g. posters, fliers) will be used? - *attach all materials*

Methods of recruitment will include letters and a brochure.

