Patients enrolled in the study will be informed that the research data collection will add about an hour to their current clinical visit. However, patients will gain information about their exercise capacity.

Table 1 Data Collection Schedule

Measures	Baseline visit	12-week visit	Minutes
Height, weight, blood pressure	X	X	10
Arterial Stiffness	X	X	20
Fasting lipids, glucose, insulin, HgnA1C, CRP, ALT	X	X	20
Accelerometry	X	X	10
Questionnaires	X	X	20
Chart Review for Medical History	X	X	20
Study Total			100

g. Study Timeline (as applicable)

See Table 2. Study recruitment will start in April of 2011 and continue until target enrollment is reached or funding is exhausted.

Table 2 Study Timeline (2011)

Study Event	Mar	Apr	May	Jun	Jul	Aug	Sep	Oct	Nov	Dec	Jan	Feb	Mar
Recruitment		X	X	X	X	X	X	X	X	X			
Consent/ Baseline		X	X	X	X	X	X	X	X	X			
Patient Follow-up		X	X	X	X	X	X	X	X	X			
12-Week Assessment					X	X	X	X	X	X	X	X	X

h. Adverse Event Criteria and Reporting Procedures

Adverse events are not anticipated as part of this intervention based on the nature of the activity involved. Serious events requiring medical attention will be reported immediately to Drs. [name] and [name] as well as to CCI per the reporting policy.

- i. If the Investigator is the Sponsor/Assignee (IND or IDE-holder), he/she is responsible for selecting a qualified monitor who will monitor the progress of all clinical investigations conducted under the IND or IDE. Please describe the monitoring plan for this protocol below:**

↳ Note: the EQuIP office provides monitoring services and advice. For info, contact EQuIP @ [name].

Not applicable

5. Data Management and Statistical Analysis

Data Management Methods

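### Does the one-week wear run-in leave 60 recruited patients short of the 30 per study group in Section 5d?

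*Combined protocol and SAP*

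**What the plan says.** All places are in the combined protocol and SAP.

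- **Section 4b (Patient Selection):** "A sample of 60 patients at increased risk for atherosclerosis will be recruited from Preventive Cardiology".
- **Section 4a (Study Design):** every participant wears the device for a week, and then "patients who have worn the accelerometer for more than 8 hours per day for at least 3 days will be randomly assigned".
- **Section 4c (Recruitment Methods):** at the clinic visit, "If eligible we will obtain consent for enrollment into the study". There is also a telephone route: verbal consent, device sent by post, written consent at the first study visit. A small payment is made "when they qualify and arrive at their first study visit".
- **Section 4g (Study Timeline):** recruitment will "continue until target enrollment is reached or funding is exhausted".
- **Section 5d (Study sample size):** 40 completers, 20 per group, are said to give "adequate power to detect differences in physical activity counts as small as 0.9 standard deviations". Attrition is put at no more than 30%, and the text continues: "attrition rate over 6 months: 30 patients per study group will be enrolled to ensure" at least 20 completers in each group.
- **Section 5c (Data Analysis Plan):** "The primary test of hypothesis is the comparison of change in Energy Expenditure", from baseline to 12 weeks, by a two-sample t-test at two-sided 0.05.

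The plan gives no expected run-in failure rate, no rule for replacing run-in failures and no separate consent target.

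**The concern.** The number recruited equals the number to be placed in groups, yet a filter stands between the two. Read literally, 60 recruits give 30 per group only if nobody fails the wear week. The 30% allowance is worded per study group, and groups exist only after randomisation, so it appears to be spent already in going from 30 to 20. The margin is one completer per group. The payment condition in Section 4c suggests that the plan itself expects some patients not to qualify.

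At stake would be the power claim: with fewer than 20 completers per group, power at 0.9 SD falls below what Section 5d relies on.

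Two mismatches in the same sentences add to the impression of a loose calculation. Attrition is given over 6 months although follow-up is 12 weeks. The 0.9 SD is attached to activity counts although the primary test is on change in energy expenditure.

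**Working it through.** **Inputs.** From Section 5d: 0.9 SD, 20 completers and 30 enrolled per group, attrition at most 30%. From Section 5c: two-sided 0.05, two-sample t-test. From Section 4b: 60 recruited. Section 5d gives no numerical power, so 80% is assumed. The run-in failure share f is not in the documents and is varied.

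**1. The plan's own figures.** Normal approximation: n = 2(1.96 + 0.84)² / 0.9² = 19.4, so 20 per group. Power at n = 20 is 81.2% by the normal approximation and 79.2% by the noncentral t (38 degrees of freedom, noncentrality 0.9 x √(20/2) = 2.85). Attrition: 20 / 0.70 = 28.6, so 29; the plan uses 30, and 30 x 0.70 = 21. Section 5d reproduces.

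**2. One counting point used throughout.**
- *At consent:* 60 x 0.70 = 42 completers, or 21 per group, with run-in losses inside the 30%. The target of 40 is met, and total loss from consent could reach 1 - 40/60 = 33.3%.
- *At randomisation:* the target is 60 randomised. Section 4g continues recruitment until that is reached, so run-in failures are replaced by further recruits for as long as funds last.

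**3. Mixed counting points.** Suppose 60 is a cap on consented patients and attrition a applies only after randomisation. Completers per group = 30(1 - f)(1 - a). To keep 40 completers in total, the number randomised must be at least 40/(1 - a).

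| Attrition a | Minimum randomised | Run-in failures absorbed, of 60 |
|---|---|---|
| 30% | 57.1, so 58 | 2 |
| 20% | 50 | 10 |
| 15% | 47.1, so 48 | 12 |

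At 30%, three failures give 57/2 x 0.70 = 19.95 per group.

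Expected completers per group over an assumed range of f:

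| f | a = 30% | a = 20% | a = 15% |
|---|---|---|---|
| 10% | 18.9 | 21.6 | 22.95 |
| 20% | 16.8 | 19.2 | 20.4 |
| 30% | 14.7 | 16.8 | 17.85 |

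Noncentral-t power at 0.9 SD is 81.2% at n = 21, 79.2% at 20, 77.0% at 19, 74.6% at 18, 72.1% at 17, 69.3% at 16, 66.3% at 15 and 63.0% at 14.

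**4. Which attrition applies.** The 30% is an upper bound over 6 months, and follow-up lasts 12 weeks. If losses came at a constant rate (an assumption), 30% over 26 weeks would be 1 - 0.70^(12/26) = 15.2% over 12 weeks. That is close to the 15% column.

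**5. The variable label.** The effect is stated in SD units, so n = 20 is the same whether 0.9 SD refers to counts or to change in energy expenditure. The label does not move N.

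**The case for a change.** The strongest case for a change is textual. Section 4c uses enrolment for the consent step, which on the clinic-visit route comes before the wear week. Section 5d speaks of patients per study group, who exist only after randomisation. On those words the mixed reading is a fair one, and Section 4g does not say which count its target uses. Recruitment may also end when money runs out, so replacement is not assured. The sponsor's preliminary work (Section 3) found poor compliance with exercise prescriptions to be common, which makes zero run-in loss an optimistic default. And although this is a pilot, it makes a power claim and plans a formal test.

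Much of this stands as description: the counting point is undefined, and no failure rate or replacement rule is written down. It does not establish a shortfall.

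- Nothing caps consent at 60.
- On the telephone route, written consent can follow the wear week, and the payment condition fits equally well with non-qualifiers being treated as screening failures outside the 60.
- Compliance with an exercise prescription is not the same as wearing an armband for 3 days.
- The funding clause would limit any recruitment target, however it was worded.

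The available remedies gain little. Recruiting 60/(1 - f) would mean 67, 75 or 86 patients at 10%, 20% or 30% failure. Keeping 60 and restating the difference detectable with 80% power would give 0.93, 0.99 or 1.06 SD at 19, 17 or 15 completers per group. Each figure depends on an f that the documents do not supply, and the second set also takes the full 30% attrition.

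**Conclusion.** No change follows. The sample-size arithmetic in Section 5d is sound. A deficit needs three things together: 60 as a ceiling on consented patients, 30 per group counted after randomisation, and run-in failures beyond what the margin absorbs. That margin is 2 of 60 if the 6-month bound of 30% applies in full to 12 weeks, but 10 to 12 of 60 at 20% to 15% attrition. In the least favourable of these attrition cases with 10% run-in failure, power at 0.9 SD is 77.0% at 19 completers per group (74.6% at 18), against 79.2% at the planned 20. That is a modest loss for a pilot whose stated standard is only adequate power. Larger losses require failure rates that are pure assumption.

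What remains is a missing definition that a study team would fill sensibly, either by recruiting until 30 per group are randomised or by counting run-in losses within the 30%. Both choices meet the 20 per group, the first if funding lasts and the second if total loss from consent stays within 30%. The 6-month period and the activity-count label are clerical slips. The label leaves N unchanged, and the longer period, if it has any effect, makes the attrition allowance more cautious.
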